7.2.5.5 Patient Index Date and Specific Treatment Assessment Durations

Patient index date is defined as the date of the first treatment of posaconazole injection and/or tablet formulations.

	30
PRODUCT: MK5592	PROTOCOL/AMENDMENT VERSION NO.: 2
REVOPS ID NO: NIS102646	CORE DRC APPROVAL DATE: 18-SEP-2024
EPIDEMIOLOGY NO.(PE STUDIES ONLY): EP08047.004	

Specific treatment assessment duration for different outcomes are summarized as follows:

- Assessment for all-cause mortality for IA will occur at Day 42. Treatment may continue beyond Day 42.
- Assessment for overall response will occur at the end of treatment (for both first line and salvage treatment). Patients may continue treatment beyond 12 weeks (84 days) however assessment for response to therapy will occur at 84 days for such patients. For patients who receive less than 12 weeks of treatment, assessment will occur at the end of posaconazole treatment.

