7.3.2.1 Primary Outcomes

The primary outcome is all-cause death among proven, probable, possible IA patients who received at least 7 days of posaconazole injection and/or tablet formulations treatment through Day 42.

Death is defined as a patient with death is recorded in the medical history or death certificate can be provided through Day 42 or within Day 42. (Data cources see 7.4)

Patients with missing or 'unable to determine' dead or alive status through Day 42 will be excluded.

PRODUCT: MK5592	PROTOCOL/AMENDMENT VERSION NO.: 2
REVOPS ID NO: NIS102646	CORE DRC APPROVAL DATE: 18-SEP-2024
EPIDEMIOLOGY NO.(PE STUDIES ONLY): EP08047.004	

Secondary Outcomes 7.3.2.2

7.3.2.2.1 **Clinical response**

The clinical response of proven, probable, possible IA patients who received posaconazole injection and/or tablet formulations treatment as the first line or salvage treatment at the end of posaconazole treatment.

Clinical responses will be defined by using the 2017 Chinese guidelines for the diagnosis and treatment of invasive fungal disease in patients with hematological disorders and cancers (the fifth version) (Table 1) or by the investigator⁷(s).

⁷Considering the low compliance with guidelines in real-world clinical practice, it is possible that there may be insufficient information from medical record to support the definition of clinical response according to the guideline (Table 1). Therefore, investigator's professional judgment could be used to define the clinical response. The subgroup analysis by the methods of clinical response definition (guideline vs. investigator's professional judgment) will be conducted depending on data availability. (see 7.7.2.1)

See Table 1 for the definitions for clinical response from the 2017 Chinese guidelines for the diagnosis and treatment of invasive fungal disease in patients with hematological disorders and cancers (the fifth version). The Chinese guidelines are consistent with the 2008 EORTC/MSG guidelines.

Table 1 Clinical Response Definitions from the 2017 Chinese guidelines for the diagisnos and treatment of invasive fungal disease in patients with hematological disorders and cancers (the fifth version).

Outcome, Response	Criteria
Success	

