7.5 Study Size

All eligible IA patients will be identified and recruited from the March 2022 to Dec 2024.

55-70 cases with posaconazole treatment are expecting to be enrolled during the recruitment period for primary and secondary objectives (30-40 cases for primary objective). The estimation of sample size is based on market supply estimation and the RCT enrollment experience. The final sample size will depend on the number of patients eligible for the study in the study period. No hypothesis test and power calculation in this study. The total sample size in the final study report may be less. See Table 2, assuming 15%-50% of all-cause mortality observed through Day 42 for primary objective, the half-width of 95% confidence interval (CI) will range from 12.1%-18.7%.

Estimated number for primary objective participants	Number of Death (%)	Two-Sided 95% Confidence Interval	Half-width of 95% Confidence Interval
N=30	4.5 (15.0)	(4.7, 32.7)	14
	6 (20.0)	(7.7, 38.6)	15.4
	9(30.0)	(14.7, 49.4)	17.3
	12 (40.0)	(22.7, 59.4)	18.4
	15 (50.0)	(31.3,68.7)	18.7
N=40	6 (15.0)	(5.7, 29.8)	12.1
	8(20.0)	(9.1, 35.6)	13.3
	12(30.0)	(16.6, 46.5)	15
	16 (40.0)	(24.9, 56.7)	15.9
	20 (50.0)	(33.8, 66.2)	16.2

 Table 2
 Two-Sided 95% Confidence Intervals for All-cause Mortality

^a Based on the two-sided exact confidence interval of a binomial proportion (Clopper and Pearson, 1934).

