7.8 Data Analysis

A descriptive analysis of the distribution of values abstracted for each variable will be provided. For the continuous variables we are interested, the values of mean/median, standard deviation (SD), min/max, interquartile range (IQR, including the first quartile [Q1] and third quartile [Q3]) will be calculated; the frequency and percentages will be calculated for these categorical variables. All analyses will be carried out using all available data. A participant with missing data on one variable will be used only in calculations that do not involve that variable.

	39
PRODUCT: MK5592	PROTOCOL/AMENDMENT VERSION NO.: 2
REVOPS ID NO: NIS102646	CORE DRC APPROVAL DATE: 18-SEP-2024
EPIDEMIOLOGY NO.(PE STUDIES ONLY): EP08047.004	

All analyses will use SAS (SAS Institute Inc., Cary, North Carolina). Detailed statistical analysis plan (SAP) and corresponding mock-up tables/figures/listings will be described separately prior to the commencement of any analyses.

All analysis detailed will be described in a separate "Statistical Analysis Plan". Key points are listed below.

7.8.1 **Primary Objective**

The primary objective is to assess the all-cause mortality of using posaconazole for proven, probable, possible IA patients. The all-cause mortality will be calculated with 95% CI.

Total all-cause mortality=number of total IA patients who die through Day 42/number of all IA patients (proven, probable, possible) included in the study with dead or alive status reported x 100%.

All-cause mortality by treatment line=number of IA patients by treatment line who die through Day 42/number of IA patients by treatment line (proven, probable, possible) included in the study with dead or alive status reported x 100%.

The analysis will be stratified by method of data collection: prospective vs. retrospective.

The following subgroupanalysis may be conducted depending on data availability:

- 1. Treatment duration (e.g. group by median treatment duration, etc);
- 2. Patients who only receive Posaconazole injection vs patients who receive Posaconazole injection then Posaconazole tablet;
- 3. Risk factors for mortality and poor outcome (Allogeneic hematopoietic stem cell transplant (HSCT); Relapsed leukemia, undergoing salvage chemotherapy; Liver transplant recipients)
- 4. IA at sites: Pulmonary IA vs others (sinus/upper respiratory involvement or disseminated disease to other organs).

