7.8.2 Secondary Objectives

7.8.2.1 Overall response rates of posaconazole injection and/or tablet by treatment line at the end of posaconazole treatment

The secondary objective is to assess the overall response rates of using posaconazole for proven or probable or possible IA patients by treatment line. The Numerator is the success response of posaconazole which include survival followed by either complete response (CR) or partial response (PR) definition by treatment line (first line or salvage). The overall response rates at the end of posaconazole treatment will be described by percent with 95% CI in the patients with proven or probable or possible IA patients by treatment line.

Overall response rates (ORRs)=(number of patients with CR or PR) by treatment line (first line or salvage treatment)/ number of IA patients included in the study with available evidence on treatment response at the end of treatment by treatment line (first line or salvage treatment) x 100%.

The analysis will be stratified by method of data collection: prospective vs. retrospective.

The following subgroup analysis may be conducted depending on data availability:

- 1. Treatment duration;
- 2. Patients who only receive posaconazole injection vs patients who receive posaconazole injection then posaconazole tablet;
- 3. Risk factors for mortality and poor outcome (Allogeneic hematopoietic stem cell transplant (HSCT); Relapsed leukemia, undergoing salvage chemotherapy; Liver transplant recipients; HSCT+Hematologic Malignancy vs. all other immunocompromised vs. No recorded risk factor (if any));
- 4. IA at sites: Pulmonary IA vs others (sinus/upper respiratory involvement or disseminated disease to other organs);
- 5. Methods of clinical response definition: guideline vs. investigator judgment.

The following sensitivity analysis may be conducted depending on data availability:

Merge analysis of data from both prospective and retrospective collection.

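### The injection-only versus injection-then-tablet subgroup in 7.8.1 sorts patients by a switch made after time zero, so step-down mortality is expected to look lower with no true difference

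*Protocol*

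**What the plan says.** Section 7.8.1 defines the primary measure as a crude proportion: "Total all-cause mortality=number of total IA patients who die through Day 42/number of all IA patients" whose vital status is known. It then says "The following subgroupanalysis may be conducted depending on data availability", and item 2 of that list is "Patients who only receive Posaconazole injection vs patients who receive Posaconazole injection then Posaconazole tablet". Section 7.8.2.1 repeats the split for overall response: "Patients who only receive posaconazole injection vs patients who receive posaconazole injection then posaconazole tablet". Neither place says when membership is fixed.

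Time zero is in 7.2.5.5: "Patient index date is defined as the date of the first treatment of posaconazole injection and/or tablet formulations". The same section says that assessment of mortality "for IA will occur at Day 42. Treatment may continue beyond Day 42". Entry is restricted in 7.3.2.1 to patients "who received at least 7 days of posaconazole injection and/or tablet formulations treatment through Day 42". Section 7.5 expects "30-40 cases for primary objective", assumes 15% to 50% mortality, and plans no hypothesis test.

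For response, 7.1 and 7.3.2.2.1 require 42 to 84 days of treatment in first-line patients and 7 to 84 days in salvage patients.

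**The concern.** Both groups start on injection. What separates them is whether a change to tablet happened before death or the end of treatment, which is unknown at the index date. The time a step-down patient lived before switching is guaranteed survival. Deaths before an intended switch all fall to the injection-only group. Group membership is therefore partly determined by the outcome.

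The minimum of 7 days' exposure makes everyone a survivor to about Day 7, but nothing requires the switch to have happened by then. Section 7.10 names immortal time bias only for survivors being easier to reach for consent and for unknown vital status. Its remedies, contacting relatives and close monitoring, do not touch this comparison.

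This is the only contrast between formulation patterns in the plan. A table of two mortality figures with confidence intervals could show a survival advantage for step-down that the grouping rule itself produced.

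**Working it through.** **The plan's own figure.** Table 2 in 7.5 reproduces with exact Clopper-Pearson limits: 6 deaths in 40 gives 5.7% to 29.8% (half-width 12.1), and 15 in 30 gives 31.3% to 68.7% (half-width 18.7). The protocol gives no figure for the subgroup.

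**Inputs.** From the protocol: time zero at first dose, deaths through Day 42, at least 7 days of exposure, mortality 15% to 50%. Assumed because the protocol is silent: a constant hazard from index, intended switch day uniform over a window, and a share who would never switch. Under the null, the switch has no effect and its timing is independent of prognosis.

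**Formulas.** Let M be Day-42 mortality from index, λ = −ln(1−M)/42 and S(t) = exp(−λt). Condition on being alive at Day 7.

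- P = S(42)/S(7), survival from Day 7 to Day 42.
- q = share intended to switch.
- A = average over the switch window of survival from Day 7 to the switch day (taken as 1 for switch days up to 7).
- Step-down share = qA, and step-down deaths = qA − qP.
- Injection-only share = 1 − qA, and injection-only deaths = (1 − P) − (qA − qP).

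**Worked case:** M = 30%, switch Day 7-28, 30% never switch.

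- λ = 0.3567/42 = 0.00849 per day; S(7) = 0.9423; P = 0.70/0.9423 = 0.7429; overall mortality = 25.7%.
- A = (1 − exp(−21λ))/(21λ) = 0.1633/0.1783 = 0.916.
- Step-down share = 0.7 × 0.916 = 0.641; deaths = 0.641 − 0.7 × 0.7429 = 0.121; mortality = 0.121/0.641 = 18.9%.
- Injection-only share = 0.359; deaths = 0.257 − 0.121 = 0.136; mortality = 0.136/0.359 = 37.9%.

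**Range at M = 30%, no true difference:**

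| Switch window | Never switch | Injection only | Step-down | Gap (points) |
|---|---|---|---|---|
| All by Day 7 | any | 25.7% | 25.7% | 0 |
| Day 3-10 | 30% | 26.6% | 25.3% | 1.3 |
| Day 7-14 | 50% | 27.8% | 23.5% | 4.3 |
| Day 7-21 | 20% | 39.5% | 21.2% | 18.3 |
| Day 7-28 | 30% | 37.9% | 18.9% | 19.0 |
| Day 10-30 | 10% | 61.5% | 17.1% | 44.4 |

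The Day 7-28 case gives 20.0% vs 9.1% at M = 15%, and 58.8% vs 33.6% at M = 50%.

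**Alternative reading of the mortality input.** Table 2's percentages describe study participants, who have already survived to about Day 7. With 30% mortality from Day 7 to Day 42, 75% intended to switch and Day 7-21, simulation gives 42.0% vs 24.9%, so the conclusion is the same.

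**Single studies.** With 30 to 40 patients, 75% intended to switch and Day 7-21, step-down mortality came out lower in about 70% to 89% of simulated null studies across 15% to 50% mortality.

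**Effect of a Day-14 landmark.** Among patients alive at Day 14, both groups have expected mortality 1 − S(42)/S(14), which is 21.2% vs 21.2% at M = 30%. Simulated null gaps were within 0.3 points. The share of deaths that leaves the table is (S(7) − S(14))/(S(7) − S(42)): 21.1%, 22.4% and 24.9% at M = 15%, 30% and 50%.

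**Response.** Every first-line patient in the response set has been treated for at least 42 days, so a switch before Day 42 confers no guaranteed survival that the other group lacks. Salvage patients may enter with 7 days, and death counts as failure in Table 1, so the mechanism remains there. No response rate was simulated.

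**The case against.** The strongest reply is that the table is optional, descriptive and small, that no hypothesis is tested, and that no objective compares formulations. All of that stands. It limits the consequence to this subgroup and rules out saying that step-down mortality will be lower in the study: the bias holds in expectation, not in every sample of 30 to 40.

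Second, the 7-day minimum removes the bias from early switches, and the protocol gives no switch timing. This also stands. The gap may be near zero, and the 44-point case needs 90% of patients due to switch and none before Day 10.

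Third, 7.8 says details will be in a separate SAP, which could fix the classification time. It could, but the protocol names the two groups by what was received over the whole course, and a SAP that follows that wording inherits the problem. This is a stated rule that misleads, not an omitted detail.

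A reader might also infer that the overall Day-42 mortality is biased by this rule. It is not, since that estimate does not use the split. Nor does the problem carry over in full to 7.8.2.1: the 42-day minimum largely cancels it for first-line response.

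**Conclusion.** The point holds for the mortality subgroup in 7.8.1 and can apply to salvage response in 7.8.2.1. At 30% Day-42 mortality from index, the expected gap with no true difference runs from 0, through about 1 to 4 points with early switching, to 18 to 19 points with switching over two to three weeks after Day 7. It reaches about 44 points in an extreme case. These figures rest on a constant hazard, switching unrelated to prognosis, and assumed switch windows and never-switch shares. The direction does not depend on the particular values, provided some switches fall after about Day 7. If patients are moved to tablets because they are improving, the gap would widen further, but that is confounding and a separate matter. The change is worth making before analysis. It does not threaten the primary result.

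**What to change.** In 7.8.1, subgroup 2, state that patients are classified by whether they have switched to tablet by a prespecified landmark day (Day 14 is an illustration) among those alive on that day, and that only deaths after the landmark through Day 42 are counted. In 7.8.2.1, apply the same rule to salvage patients who are alive and not yet assessed for response at the landmark, with response assessed after it. Label both tables descriptive, and say that improvement-driven switching remains as confounding, which a landmark does not remove.

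The cost is a reworded line in each section. About 21% to 25% of deaths, those before the landmark, drop out of that mortality table only. Patients who switch later count as not yet switched, and salvage patients assessed before the landmark leave the response table. Section 7.3.2.2 already lists regimen, duration and death date; the case report form must also date each formulation.

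Grouping by the formulation given on the index date would avoid the bias, but it puts both of these groups together as injection starters. It answers a different question and is not a substitute.

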7.8.2 Secondary Objectives

7.8.2.1 Overall response rates of posaconazole injection and/or tablet by treatment line at the end of posaconazole treatment

The secondary objective is to assess the overall response rates of using posaconazole for proven or probable or possible IA patients by treatment line. The Numerator is the success response of posaconazole which include survival followed by either complete response (CR) or partial response (PR) definition by treatment line (first line or salvage). The overall response rates at the end of posaconazole treatment will be described by percent with 95% CI in the patients with proven or probable or possible IA patients by treatment line.

Overall response rates (ORRs)=(number of patients with CR or PR) by treatment line (first line or salvage treatment)/ number of IA patients included in the study with available evidence on treatment response at the end of treatment by treatment line (first line or salvage treatment) x 100%.

The analysis will be stratified by method of data collection: prospective vs. retrospective.

The following subgroup analysis may be conducted depending on data availability:

- 1. Treatment duration;
- 2. Patients who only receive posaconazole injection vs patients who receive posaconazole injection then posaconazole tablet;
- 3. Risk factors for mortality and poor outcome (Allogeneic hematopoietic stem cell transplant (HSCT); Relapsed leukemia, undergoing salvage chemotherapy; Liver transplant recipients; HSCT+Hematologic Malignancy vs. all other immunocompromised vs. No recorded risk factor (if any));
- 4. IA at sites: Pulmonary IA vs others (sinus/upper respiratory involvement or disseminated disease to other organs);
- 5. Methods of clinical response definition: guideline vs. investigator judgment.

The following sensitivity analysis may be conducted depending on data availability:

Merge analysis of data from both prospective and retrospective collection.

7.8.2.2 Baseline Demographic and Clinical Characteristics by treatment line

The variables list in Section 7.3.2.2.2 Demographic and Clinical Characteristics will be described among patients in the study population overall, and separately by treatment line.

	41
PRODUCT: MK5592	PROTOCOL/AMENDMENT VERSION NO.: 2
REVOPS ID NO: NIS102646	CORE DRC APPROVAL DATE: 18-SEP-2024
EPIDEMIOLOGY NO.(PE STUDIES ONLY): EP08047.004	

7.8.2.3 Treatment Patterns by treatment line

The variables list in Section 7.3.2.2.3 Treatment Patterns will be described among patients in the study population overall, and separately patients by treatment line.

For discontinuation characteristics, frequency, proportion of patients with discontinuation, and time taken from the initiation to discontinuation will be reported. The reason for discontinuation will be classified and reported.

7.9 Quality Control

By signing this protocol, all parties agree to following applicable standard operating procedures (SOPs). All parties also agree to ensuring all existing and new study personnel are appropriately trained to ensure the study is conducted and data are generated, documented, and reported in compliance with the protocol, Good Pharmacoepidemiology Practice (GPP), Good Pharmacovigilance Practices (GVP) and all applicable, state, and local laws, rules and regulations. All parties should maintain transparency and open communication in order to effectively manage the study and proactively mitigate any risks.

The Sponsor may conduct routine or for-cause audits to ensure oversight and conduct of the study are completed in accordance with the protocol, quality standards (e.g. GPP and GVP), and applicable laws and regulations. If a significant quality issue (SQI) is identified at any time during the conduct of the study, it must be escalated to the Sponsor immediately. A SQI is any issue with the potential to negatively impact, either directly or indirectly, the rights, safety and well-being of patients or study participants and/or the integrity of the data. In the event an audit or SQI results in corrective or preventive actions, all parties are expected to appropriately implement the action plan in a timely manner.

For retrospective data, the data will be assessed in terms of the integrity and completeness. The data will be collected and entered into EDC by trained study personnel, will be reviewed for compliance with medical record writing specifications and with reasonable ranges of clinical variables by investigators. All data will be monitored by assigned qualified study research associates by source data verification, For data with logical errors, abnormal values or missing values, the investigator will be consulted on the possible causes of low data integrity and an effective data management plan will be proposed.

7.10 Limitations of the Research Methods

As this is an observational study, potential bias cannot be ruled out. Data collection will reflect routine clinical practice rather than mandatory assessments at prespecified time points, which may have an impact on the amount of data available and its interpretation. Potential sources of bias and limitations as well as strategies to minimize these are discussed further below.

First, cases from the potential leading site or potential sub sites may be sicker as these potential sites are the top-level hospitals in China. Patient with sicker situation in China

PRODUCT: MK5592	PROTOCOL/AMENDMENT VERSION NO.: 2
REVOPS ID NO: NIS102646	CORE DRC APPROVAL DATE: 18-SEP-2024
EPIDEMIOLOGY NO.(PE STUDIES ONLY): EP08047.004	

prefer top-level hospitals. Sicker cases will lead to lower ORR and higher ACM which may not reflect the real value of posaconazole. (Admission rate bias) To mitigate this bais, the following action will be implemented. The study design to assess the study outcomes (see 7.3.2) by different treatment lines (first line and salvage treatment) to differentiate patients' disease conditions. Patient characteristics by treatment line are also described as secondary endpoint.

Second, survivor cases from retrospective data collection are easier to be reached to sign the ICF in the recruitment period, at the same time, cases from retrospective data collection or prospective data collection may be lost to follow-up without clear alive or dead status or response data. These situations will lead to underestimate or overestimate the ACM/ORR. (Immortal time bias/ No-respondent bias/Survivor bias) To mitigate this bias, study design to contact not only the case himself/herself from retrospective data collection, but also their relatives to follow up with missing dead or alive status. And cases from prospective data collection will be closed monitor to make sure the alive or dead status and response data are recorded.

Third, for cases from retrospective data collection, some historical clinical data may be missing. (Missing clinical data bias) The missing data may be correlated with the outcome (e.g., perhaps more clinical data is included for more severe cases that require more frequent monitoring, which would lead to underrepresentation of less severe cases that are more likely to survive) such that estimates could be biased. Case with missing critical data, for example, missing withdead or alive status at day 42/ information of treatment responsed after the end of treatment, will be excluded from the ACM and ORR calculation, so the sample size will be smaller than estimation.

this may impact on the patient number received posaconazole injection and/or tablet. To ensure the completeness of clinical data, cases without treatment response or classification of proven, probable, possible will require doctor's judgement about whether the treatment response and classification can be defined by the other examination/test reports previously to minimum the missing data rate.

Fourth, the selected hospitals or patients will not be randomly selected and may not be a representative sample of the whole posaconazole injection and/or tablet formulations. The hospital selection will based on the operation difficulty, potential number of IA patients and potential use of posaconazole injection and/or tablet formulations. This study aim to select hospital with more potential IA patients and use of posaconazole injection and/or tablet formulations to present the representativeness.

